6.12.6. Pump-related Safety Analyses

6.12.6.1. Time Until Infusion Set Changes

Date and time of all infusion set changes will be captured in the eCRF. Time interval in hours until infusion set change for each infusion set can be derived through a time-to-day conversion by dividing the time difference between the infusion set change and its previous infusion set change by 86400 seconds.

The protocol requires the patients to change infusion set every 3 days unless a change is required for failure of the infusion set. The eCRF captures both the planned and unplanned infusion set changes. For unplanned infusion set changes, BG, the reason for change and ketone test result (when SMBG > 300 mg/dL) will also be captured.

For the entire study period (including lead-in), time to infusion set changes in hours for overall, planned and unplanned infusion set changes will be derived and analyzed. Infusion set changes at MMTT will be excluded in calculating time until infusion set changes, because this change is

a study procedure and does not reflect the patients' behavior. The average time to infusion set change, measured in days, for the following time intervals: (-2)- to 0, 0 to 4, 4 to 8, and 8 to 16 weeks, mapped to Weeks 0, 4, 8, and 16, respectively, will be analyzed using an MMRM model similar to the model used for the primary endpoint. The average time to infusion set change across the entire 0 to 16 weeks will be analyzed using an ANCOVA model.

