20. To compare LY900014 and Humalog with respect to quality of life as measured by the EQ-5D-5L	20. Change from baseline in EQ-5D-5L UK-population-based health state index score and EQ-VAS score at Week 16.
21. To compare LY900014 and Humalog with respect to diabetes treatment satisfaction as measured by the ITSQ	21. Change from baseline in ITSQ regimen inconvenience and lifestyle flexibility domain scores at Week 16

22. To compare LY900014 and Humalog with respect to changes in body weight	22. Change in weight (kg) from baseline to Week 16
23. To compare LY900014 and Humalog with respect to the time interval until infusion set change	23. Time interval until infusion set change during the 16-week treatment period
24. To compare LY900014 and Humalog with respect to the factors affecting dosing in pumps	24. Actual and change from baseline in factors affecting dosing in pump (CR, ISF, AIT, and frequency of use of non-normal bolus type [Square Wave or Dual Wave]), during the 16-week treatment period
25. To compare LY900014 and Humalog with respect to the proportion of patients achieving improvement from baseline in HbA1c targets	25. The proportions of patients with shifts in HbA1c to <8% and ≤9%, from baseline to Week 16
26. To compare LY900014 and Humalog with respect to glycemic variability	26. Within-day and between-day glycemic variability measured by the standard deviation and the coefficient of variation of 10-point SMBG profiles
27. To compare LY900014 and Humalog with respect to the incremental AUCs after all meals, obtained from CGM use	27. Incremental $AUC_{0-1\text{ hour}}$ and incremental $AUC_{0-2\text{ hour}}$ after all meals from each 14-day CGM session at Week 16
28. To compare LY900014 and Humalog with respect to the glucose profiles, obtained from CGM use	28. Average glucose for a 24-hour period from each 14-day CGM session at Week 16
29. To compare LY900014 and Humalog with respect to the glucose variability, obtained from CGM use	29. Interquartile range, CV, LBGI, and HBGI from each 14-day CGM session at Week 16

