6.12.6.2. Infusion Set Changes

To handle potential missing input in paper diary for the infusion set changes, time intervals until infusion set change that are greater than 7 days (168 hours) will be excluded from the analysis. If 2 planned infusion set changes happened on the same day at the same time, only 1 will be used for analysis. The same rule applies when there are duplicate unplanned infusion set changes.

The incidence (percent of patients with at least 1 event) and rate for overall, planned and unplanned infusion set changes will be analyzed using Fisher's exact test and Wilcoxon signed-rank test respectively. The unplanned infusion set changes will be analyzed for any reason and for each individual reason (pump occlusion alarm, unexplained high BG, infusion site reaction (pain, redness or swelling at infusion site), infusion set problem (infusion set kinked, pulled out, leaking, reservoir empty, etc.). The unplanned infusion set changes will also be summarized by infusion set wear day (Day1 = \leq 24 hours, Day2 = $>$ 24 and \leq 48 hours, Day3 = $>$ 48 and \leq 72 hours and Day3+ = $>$ 72 hours) by treatment and treatment comparison will only be conducted when there are sufficient number of patients in each treatment arm. A listing of all unplanned infusion set changes will be generated for the enrolled population. For each unplanned infusion set change, the following information will be provided:

- Cannula length at study entry
- Cannula length at the time of the infusion set change
- BG at time of infusion set change
- the reason for the infusion set change
- the infusion set wear day on which the infusion set change occurs
- the ketone test value associated with the infusion set change when SMBG $>$ 300 mg/dL

A table will be generated to summarize number of patients who have at least 1 unplanned infusion set change due to unexplained high BG with BG (SMBG) $>$ 250 mg/dL (13.9 mmol/L) and with BG (SMBG) $>$ 300 mg/dL (16.7 mmol/L).

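### The average time to unplanned infusion set change is conditional on failure and barely responds to the failure hazard, so a null result must not be read as equal set durability

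*SAP*

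**What the plan says.** SAP 6.12.6.1 derives an interval for each infusion set, from the previous change to its own change, and states that "time to infusion set changes in hours for overall, planned and unplanned infusion set changes will be derived and analyzed". The schedule behind these intervals is given in the same section: "The protocol requires the patients to change infusion set every 3 days unless a change is required for failure of the infusion set".

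Two models follow. Average time in the periods -2 to 0, 0 to 4, 4 to 8 and 8 to 16 weeks "will be analyzed using an MMRM model similar to the model used for the primary endpoint". For the whole treatment period, "The average time to infusion set change across the entire 0 to 16 weeks will be analyzed using an ANCOVA model". Changes made for the mixed meal tolerance test (MMTT) are left out of the interval calculation. SAP 6.12.6.2 adds that "time intervals until infusion set change that are greater than 7 days (168 hours) will be excluded from the analysis". Neither section mentions Kaplan-Meier, Cox or any censoring rule.

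The endpoint is exploratory objective 23 in SAP Table ITRO 4.1: "Time interval until infusion set change during the 16-week treatment period". Separately, SAP 6.12.6.2 covers frequency: "The incidence (percent of patients with at least 1 event) and rate for overall, planned and unplanned infusion set changes will be analyzed". It adds: "The unplanned infusion set changes will also be summarized by infusion set wear day".

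**The concern.** A set that has not failed is removed at about Day 3, so a planned change ends observation of that set's time to failure. Without a censoring rule, a separate average for unplanned changes can use only the sets that failed. Patients with no unplanned change contribute nothing to it. Comparing arms on that average compares two groups selected by an event after randomisation. The value is also largely fixed by the 3-day schedule, because failures that must fall within a 72 h window average a little under half that window when failures are uncommon and the hazard is roughly constant.

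What is at stake is how the result is read. The analysis sits under pump-related safety. A reported absence of difference in time to unplanned change invites the conclusion that sets last equally well on both insulins, and this comparison cannot support that conclusion.

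**Working it through.** **Inputs from the documents.** Planned change every 3 days, so τ = 72 h (SAP 6.12.6.1). Approximately 420 randomised 1:1, so 210 per arm (SAP 5.2 and 5.3; used only in the simulation). The plan states no failure rate, effect size or power for this endpoint, so it has no figure to reproduce.

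**Assumptions.** Constant failure hazard h. A fraction p of sets fails by 72 h in the reference arm, varied from 2% to 30%. The hazard is doubled in the other arm, where the failing fraction becomes 1 - (1 - p)².

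**Formulas.**
- h = -ln(1 - p)/72 per hour
- Mean over failed sets: E[T | T < τ] = 1/h - τ·exp(-hτ)/(1 - exp(-hτ))
- Mean over all sets: E[min(T, τ)] = (1 - exp(-hτ))/h
- Unplanned changes per 30 days: 720h

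**Worked case, p = 5%.** hτ = -ln(0.95) = 0.05129, so 1/h = 72/0.05129 = 1403.7 h. The mean over failed sets is 1403.7 - 72 × 0.95/0.05 = 1403.7 - 1368.0 = 35.7 h. With the hazard doubled, 1/h = 701.85 h and the mean is 701.85 - 72 × 0.9025/0.0975 = 701.85 - 666.46 = 35.4 h.

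**Results when the hazard doubles.**

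| Sets failing by 72 h | Mean over failed sets (h) | Change | Mean over all sets (h) | Unplanned changes per 30 days |
|---|---|---|---|---|
| 2% | 35.88 to 35.76 | -0.3% | 71.28 to 70.56 | 0.20 to 0.40 |
| 5% | 35.69 to 35.38 | -0.9% | 70.18 to 68.43 | 0.51 to 1.03 |
| 10% | 35.37 to 34.74 | -1.8% | 68.34 to 64.92 | 1.05 to 2.11 |
| 20% | 34.66 to 33.33 | -3.8% | 64.53 to 58.08 | 2.23 to 4.46 |
| 30% | 33.86 to 31.76 | -6.2% | 60.56 to 51.48 | 3.57 to 7.13 |

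The mean over failed sets is close to τ/2 - hτ²/12, that is, 36 h less a small term. At p = 5% this is 36 - 0.05129 × 72/12 = 35.7 h. The hazard enters only through the small term.

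**Sensitivity.** With Weibull failure times of shape 0.7 to 3, the change is -0.1% to -2.2% when 2% to 10% fail, and at most -7.8% (shape 0.7, 30% failing). Letting the planned change vary around 72 h with an SD of 8 h gives the same picture: at 10% failing, 35.8 to 35.1 h.

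**Simulated power against a doubled hazard.** The simulation had 210 patients per arm, 16 weeks, gamma frailty with variance 0.5, the variable planned change time, and 300 runs. Patient means were compared by t-test, as a simple stand-in for the planned models. Rates were compared by a rank-sum test.

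| Measure | 5% failing | 10% failing |
|---|---|---|
| Mean over failed sets | 7% | 10% |
| Mean over all sets | about 100% | about 100% |
| Rate of unplanned changes | about 100% | about 100% |

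The first row is close to the 5% test level.

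**The case against.** The strongest reply is that failure frequency is already covered. SAP Table ITRO 4.1 makes the incidence and 30-day rate of unplanned changes for occlusion alarms (objective 16) and for unexplained hyperglycemia (objective 17) secondary endpoints. Protocol 10.3.4 gives negative binomial and logistic models for the alarms. SAP 6.12.6.2 analyses incidence and rate for any reason and for each reason. The overall mean in SAP 6.12.6.1 includes every set apart from those excluded by rule, and it shortens as failures rise. All of this stands. A reader might infer that the trial could miss a doubling of set failures; the documents do not support that. One caution is that SAP 6.12.6.2 names a Wilcoxon signed-rank test for the rate, which is a paired test. The simulated power for the rate assumes a rank-sum test between independent arms.

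It can also be said that objective 23 concerns wear time rather than survival of the set, and that the timing of failures is of interest in itself. This stands in part. With 5% failing, the mean over failed sets is 29.3 h for Weibull shape 0.7 and 53.8 h for shape 3, so it does respond to when failures occur. It remains a comparison of groups selected after randomisation and carries almost nothing about how often sets fail.

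Finally, the two model sentences in SAP 6.12.6.1 do not name the unplanned subset, and the section does not say that only failed sets are averaged. Both are inferences. They are the natural reading, because overall, planned and unplanned times are all to be analysed, averages are the only method given, and there is no censoring rule.

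**Conclusion.** The point holds as a limited one. On the natural reading, the unplanned component of SAP 6.12.6.1 is conditional on failure. A doubled hazard changes it by between -0.3% and -6.2% for assumed failure fractions of 2% to 30%, under a constant hazard and a 72 h planned change. The result is robust to Weibull shapes from 0.7 to 3 and to variation in the planned change time; the mean becomes more responsive only when many sets fail. The failure fractions are assumptions throughout.

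The consequence is confined to an exploratory objective. Other planned analyses would show a doubled failure rate, but none of them estimates set survival: the wear-day summary describes failures without a stated denominator of sets still in use. The remaining risk is that a null result for time to unplanned change is taken as evidence of equal set durability.

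**What to change.** In SAP 6.12.6.1, for unplanned changes, analyse each set's wear time as time to event, with planned and MMTT changes censored. Use Kaplan-Meier curves by arm and a Cox model with patient-clustered variance. State the assumption that planned changes are non-informative censoring. It could fail if, for example, patients who suspect a problem change the set early and record the change as planned. Say also how intervals over 168 h enter this analysis.

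Keep the MMRM and ANCOVA of averaged intervals for overall wear time. Report any mean among unplanned changes as descriptive and conditional on failure, without a between-arm test.

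The cost is one additional analysis and a paragraph of SAP text. Dates, times and planned or unplanned status are already captured in the eCRF, so no new data are needed. The downside is reliance on the censoring assumption.

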6.12.6.2. Infusion Set Changes

To handle potential missing input in paper diary for the infusion set changes, time intervals until infusion set change that are greater than 7 days (168 hours) will be excluded from the analysis. If 2 planned infusion set changes happened on the same day at the same time, only 1 will be used for analysis. The same rule applies when there are duplicate unplanned infusion set changes.

The incidence (percent of patients with at least 1 event) and rate for overall, planned and unplanned infusion set changes will be analyzed using Fisher's exact test and Wilcoxon signed-rank test respectively. The unplanned infusion set changes will be analyzed for any reason and for each individual reason (pump occlusion alarm, unexplained high BG, infusion site reaction (pain, redness or swelling at infusion site), infusion set problem (infusion set kinked, pulled out, leaking, reservoir empty, etc.). The unplanned infusion set changes will also be summarized by infusion set wear day (Day1 = \leq 24 hours, Day2 = $>$ 24 and \leq 48 hours, Day3 = $>$ 48 and \leq 72 hours and Day3+ = $>$ 72 hours) by treatment and treatment comparison will only be conducted when there are sufficient number of patients in each treatment arm. A listing of all unplanned infusion set changes will be generated for the enrolled population. For each unplanned infusion set change, the following information will be provided:

- Cannula length at study entry
- Cannula length at the time of the infusion set change
- BG at time of infusion set change
- the reason for the infusion set change
- the infusion set wear day on which the infusion set change occurs
- the ketone test value associated with the infusion set change when SMBG $>$ 300 mg/dL

A table will be generated to summarize number of patients who have at least 1 unplanned infusion set change due to unexplained high BG with BG (SMBG) $>$ 250 mg/dL (13.9 mmol/L) and with BG (SMBG) $>$ 300 mg/dL (16.7 mmol/L).

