Hypoglycemia rates will be summarized for periods of 1 year and 100 years (severe hypoglycemia only). The rate of severe hypoglycemia per 100 years will be compared between treatment groups using the empirical method. For each of the other categories of hypoglycemia, the number of hypoglycemia events during a specific period (rate) after randomization (for example, 0- to 4 weeks of treatment period) will be analyzed by using a negative binomial regression model including treatment. An offset defined as the log transformation of treatment exposure in the specific period (days)/365.25 days will be included in the model to estimate the rate of hypoglycemia per year. The proportion of patients with at least 1 hypoglycemic event in each category (incidence) during a specific period after randomization will be analyzed using a logistic regression model including treatment.

Similarly, a negative binomial model and a logistic regression model including treatment will be used to analyze the rate of pump occlusion alarms leading to unplanned infusion set changes per 30 days, and the proportion of patients with at least 1 occlusion alarm (incidence) leading to unplanned infusion set changes, respectively.

Continuous safety variables, as well as the change from baseline for these variables, will be analyzed by MMRM or ANCOVA models. For categorical variables, Fisher's exact test or Pearson's chi-square test will be used to compare treatment groups unless otherwise specified.

Change from baseline to last-observation-carried-forward endpoints for European Quality of Life – 5 Dimensions 5 Level (EQ-5D-5L) and ITSQ will be analyzed using ANCOVA models.

2. Schedule of Activities

Table ITRO.1. Schedule of Activities

Study Procedure	Study Screening	Lead-In Period		Treatment Period											Safety Follow-up	ED
		1	2	3	4	5 ^a	6	7 ^a	8	9	10	11	12	13		
eCRF Visit Number	1	2	3	4	5 ^a	6	7 ^a	8	9	10	11	12	13	801	ED ^b	
Visit Window (± days)		3	3	3	3	3	3	3	7	7	7	7	7	7	7	
Time on Study Relative to First Active Treatment Dose (weeks)	-3	-2	-1	0	1	2	3	4	6	8	12	14	16	20		
Study Logistics																
Informed consent signed	X															
IWRS	X	X	X	X	X	X	X	X	X	X	X	X	X	X	X	X
Patient eligibility review	X															
Randomization ^c				X												
Clinical Assessments																
Patient demographics	X															
Medical history and preexisting conditions	X															
Physical examination/height	X															

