Similarly, a negative binomial model and a logistic regression model including treatment will be used to analyze the rate of pump occlusion alarms leading to unplanned infusion set changes per 30 days, and the proportion of patients with at least 1 occlusion alarm (incidence) leading to unplanned infusion set changes, respectively.

Continuous safety variables, as well as the change from baseline for these variables, will be analyzed by either MMRM or ANCOVA models. For categorical variables, Fisher's exact test or Pearson's chi-square test will be used to compare treatment groups unless otherwise specified.

The analyses for assessing immunogenicity data will be described in the SAP after being agreed with the FDA on the threshold for determining treatment-emergent antibodies to insulin lispro.

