Figure ITRO 6.1.	Testing scheme for primary and multiplicity adjusted objectives.....	23

Table of Contents

Appendix		Page
Appendix 1.	Empirical Estimation of Relative Event Rate	47
Appendix 2.	Derivation of CGM Variables	49

3. Revision History

This statistical analysis plan (SAP) is the first version and is based on the protocol of I8B-MC-ITRO approved on 17 October 2018 and the following amendments (a), (b) and (c) approved on 28 March 2019, 21 June 2019, and 8 October 2019 respectively. This SAP was approved prior to the unblinding of the treatment assignments.

Statistical analysis plan (SAP) Version 2 was approved prior to first unblinding and database lock. The main changes are listed below:

1. For the continuous glucose monitoring (CGM) analyses, clarified the rules for defining data on investigational product (IP), the derivation of CGM endpoints for Visit 10, the analysis method for CGM continuous endpoints, and the minimum percentage of patients in each subgroup to conduct treatment-by-subgroup interaction analyses; added analyses using the intention-to-treat (ITT) estimand for the multiplicity-adjusted endpoints, removed mean amplitude of glycemic excursions (MAGE), low blood glucose index (LBGI) and high blood glucose index (HBGI) from by-meal analyses, as MAGE is not relevant for by-meal analyses and LBGI and HBGI can be assessed alternatively by the other planned analyses (for example, time in range by meal).
2. Added specifications for classification of hypoglycemia events that occur within 30 minutes of each other.
3. Added specifications excluding mixed meal tolerance test (MMTT) infusion set changes from the analysis of time to infusion set change and the exclusion of time intervals >7 days from the analysis due to probable missing data.
4. Added specification for handling duplicate infusion set changes occurring at the same date and time.

4. Study Objectives

Table ITRO 4.1 shows the objectives and endpoints of the study.

Table ITRO 4.1. Objectives and Endpoints

Objectives	Endpoints
Primary Objective	
1. To test the hypothesis that LY900014 is noninferior to Humalog on glycemic control ([NIM = 0.4% for HbA1c) in patients with T1D using CSII for 16 weeks	1. Difference between LY900014 and Humalog in change from baseline to Week 16 in HbA1c
Multiplicity Adjusted Objectives	

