11. To compare LY900014 and Humalog with respect to 10-point SMBG profiles	11. Change from baseline 10-point SMBG values at Week 16
12. To compare LY900014 and Humalog with respect to total, basal, and bolus insulin dose	12. Change from baseline in bolus/total insulin dose ratio at Week 16
13. To compare LY900014 and Humalog with respect to the proportion of patients achieving HbA1c targets	13. The proportion of patients with HbA1c <7% and ≤6.5% at Week 16
14. To compare LY900014 and Humalog with respect to the duration of time spent in hypoglycemic glucose ranges, obtained from CGM use	14. Duration (in minutes) and percentage of time with glucose values <54 and <70 mg/dL (3.0 and 3.9 mmol/L), normalized to a 24-hour period and number of episodes, defined as at least 10 consecutive minutes <54 and <70 mg/dL, from each 14-day CGM session at Week 16
15. To compare LY900014 and Humalog with respect to the duration of time spent in hyperglycemic glucose ranges, obtained from CGM use	15. Duration (in minutes) and percentage of time with glucose values >180 and >250 mg/dL (10.0 and 13.9 mmol/L), normalized to a 24-hour period and number of episodes, defined as at least 10 consecutive minutes >180 and >250 mg/dL, from each 14-day CGM session at Week 16
16. To compare LY900014 and Humalog with respect to the incidence and rate of pump occlusion alarms that lead to an unplanned infusion set change	16. Rate (events/patient/30 days) and incidence (percent of patients with at least 1 event) of pump occlusion alarms that lead to an unplanned infusion set change from baseline through Week 16
17. To compare LY900014 and Humalog with respect to the incidence and rate of episodes of unexplained hyperglycemia that lead to an unplanned infusion set change	17. Rate (events/patient/30 days) and incidence (percent of patients with at least 1 event of unexplained hyperglycemia > 300 mg/dL confirmed by SMBG that leads to an unplanned infusion set change from baseline through Week 16
Tertiary/Exploratory	
18. To compare the safety of LY900014 and Humalog	18. Adverse events, vital signs, chemistry, and hematology laboratory measures
19. To compare the incidence of treatment-emergent positive anti-insulin lispro antibodies for LY900014 and Humalog	19. Incidence of treatment emergent anti-insulin lispro antibodies

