5.1. Summary of Study Design

Study I8B-MC-ITRO (ITRO) is a Phase 3, prospective, randomized, outpatient, multinational, multicenter, 2-treatment group, parallel, active-controlled, double-blind study conducted in patients with type 1 diabetes (T1D) currently using continuous subcutaneous insulin infusion (CSII) therapy. Patients will be randomized to receive LY900014 or Humalog as both basal and bolus insulin and will administer bolus doses 0 to 2 minutes prior to meal (pre-meal). The study is designed to demonstrate noninferiority of LY900014 when compared with Humalog in change in HbA1c from baseline to Week 16, when both are used via CSII and bolus doses are given prior to the start of the meal. The study periods include 1-week screening, 2-week lead-in, 16-week treatment, and a 4-week safety follow-up. [Figure ITRO 5.1](#) illustrates the study design.

Patients treated with a rapid-acting insulin analog—insulin lispro, insulin aspart, or insulin glulisine via CSII—will be eligible for inclusion in the trial. All patients will use Humalog during the lead-in period. Those treated with either insulin aspart or insulin glulisine at screening will be transferred to Humalog at Visit 2. At Visit 4, patients will be randomized to either LY900014 or Humalog with bolus doses given immediately prior to each meal. Specific elements of this study design will include collection of 10-point self-monitored blood glucose (BG), blinded CGM sessions, and Mixed Meal Tolerance Testing.

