5.3. Method of Treatment Assignment

Patients who meet all criteria for enrollment will be randomized to double-blind treatment at Visit 4. Assignment to treatment groups will be determined by a computer-generated random

sequence using an interactive web-response system (IWRS). The IWRS will be used to assign all vials containing double-blind IP during the study and open-label Humalog during the lead-in period. Site personnel will confirm that they have located the correct vials by entering a confirmation number found on the vials into the IWRS. Patients will be randomized to 1 of the 2 treatment groups in 1:1 ratio (double-blind LY900014, double-blind Humalog). Stratification will be by country, HbA1c stratum ($\leq 7.5\%$, $> 7.5\%$ at Visit 1), and patient's personal CGM or flash glucose monitoring (FGM) use during the study (yes/no). Patients will begin using double-blind IP in their pumps immediately following successful completion of the Visit 4 MMTT. Patients will fill a new pump reservoir and infusion set with IP, then insert a new pump infusion set cannula and begin infusion of IP prior to leaving the investigative site.

Abbreviation: T=Telephone Visits.

^a Pre-study rapid-acting insulins: insulin lispro, insulin aspart, insulin glulisine via CSII. At Visit 2, patients on insulin glulisine or insulin aspart will be transferred to Humalog. At Visit 4, patients will be randomized to either LY900014 or Humalog.

^b Patients will discontinue study insulins at Week 16.

Figure ITRO 5.1. Illustration of study design.

6. A Priori Statistical Methods

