6.1. General Considerations

Statistical analysis of this study will be the responsibility of Eli Lilly and Company (hereafter Lilly) or its designee. Any change to the data analysis methods described in the protocol will require an amendment ONLY if it changes a principal feature of the protocol. Any other change to the data analysis methods described in the protocol, and the justification for making the change, will be described in the SAP or the clinical study report (CSR). Additional exploratory analyses of data will be conducted, as deemed appropriate.

For purposes of analysis, the following populations are defined in [Table ITRO 6.1](#).

Table ITRO 6.1. Patient Populations

Population	Description
Entered	All patients who give informed consent.
Enrolled	All patients who receive at least 1 dose of open-label Humalog in the 2-week lead-in period.
Randomized	All patients who are randomly assigned to study treatment at Visit 4. Treatment group will be defined based on the treatment the patients are assigned.
Safety	All randomized patients who receive at least 1 dose of the randomly assigned IP. Treatment group will be defined based on the treatment the patients were assigned.

Abbreviations: IP = investigational product.

Unless otherwise stated, the efficacy analyses will be conducted on the Randomized Population and the safety analyses will be conducted on the Safety Population.

The primary analysis is for the treatment period up through Week 16.

Unless otherwise noted, all tests of treatment effects will be conducted at a 2-sided alpha level of 0.05, and CIs will be calculated at 95%, 2-sided. All tests of interactions between treatment groups and other factors will be conducted at a 2-sided alpha level of 0.10.

The definitions of baseline and post-baseline for the efficacy and safety analyses depend on which analysis period is being used. The following analysis periods will be used:

- Lead-in Period – Visits 2 to 4
- 16-Week Treatment Period – from randomization to Week 16 prior to discontinuation of IP and from randomization to Week 16 (including all data regardless of IP use)
- 16-Week Treatment Period and Safety Follow-Up Visit – from randomization to Visit 801 (including all data regardless of IP use)

The data on IP is defined based on the following rules:

- For data only measured at an office visit
 - MMTT postbaseline data will be classified as on IP if the MMTT performance date is prior to or on the last IP dose date

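### The SAP names the Wilcoxon signed-rank test, a paired or one-sample test, for comparing infusion-set-change rates between two independent arms (objectives 16 and 17), and for objective 16 it replaces the protocol's negative binomial model without giving a reason in the SAP

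*SAP*

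**What the plan says.** SAP 6.12.6.2 covers overall, planned and unplanned infusion set changes. It gives incidence to Fisher's test and rate to the signed-rank test, in that order: "exact test and Wilcoxon signed-rank test respectively". It then extends the analysis of unplanned changes to each recorded reason, including pump occlusion alarm and unexplained high glucose.

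Those two reasons correspond to objectives 16 and 17 in SAP Table ITRO 4.1. Objective 16 reads "To compare LY900014 and Humalog with respect to the incidence and rate of pump occlusion alarms that lead to an unplanned infusion set change", and objective 17 has the same form for unexplained hyperglycemia. Both endpoints are rates per patient per 30 days, plus incidence, from baseline through Week 16.

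SAP 5.1 describes a "2-treatment group, parallel, active-controlled, double-blind study conducted in patients with type 1 diabetes", and SAP 5.3 adds "Patients will be randomized to 1 of the 2 treatment groups in 1:1 ratio".

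For objective 16 the protocol is specific. Section 10.3.4 says "a negative binomial model and a logistic regression model including treatment will be used to analyze the rate of pump occlusion alarms" per 30 days. The logistic part covers "the proportion of patients with at least 1 occlusion alarm (incidence) leading to unplanned infusion set changes", and the synopsis repeats the plan. The protocol names no rate model for objective 17.

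On changes of method that do not alter a principal feature of the protocol, SAP 6.1 says that "the justification for making the change, will be described in the SAP or the clinical study report".

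**The concern.** The signed-rank test works on one set of differences: paired observations, or a single sample against a fixed value. Objectives 16 and 17 ask how two separate groups of patients differ. Taken literally, the SAP has no usable test for either rate.

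These are the pump-specific comparisons for a new formulation delivered by pump. If the text stays as it is, someone must choose the actual method after SAP approval, possibly with treatment codes in hand. Correcting the name to rank-sum would give a valid p-value but no estimate of how much more or less often set changes occur on LY900014. A per-30-day endpoint calls for that estimate.

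**Working it through.** **Plan's own figures.** The documents state no power, event rate or dispersion for objectives 16 and 17, so there is nothing to reproduce for them. The arm size follows from SAP 5.2: 368/(1 − 0.12) = 418.2, stated as about 420 randomized, or about 210 per arm at 1:1.

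**Can the named test be made to fit?** Three readings are possible.

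1. *Pair patients across arms.* The SAP defines no such pairing. Randomization is stratified, not matched, so equal arms are not guaranteed. With 212 and 208 values a two-sample call of the test returns an error. With 210 and 210 the answer depends on the pairing chosen: over 2,000 random re-pairings of one simulated data set, p ran from 2.1 × 10⁻⁶ to 6.4 × 10⁻⁴. The data were unchanged throughout.
2. *Pair each patient's lead-in with the treatment period.* SAP Table ITRO 6.2 does give unplanned set changes a baseline (Visits 2–4) and a post-baseline period (Visits 5–13), so this pairing exists. It tests change over time within an arm. Two within-arm p-values are not a test of the difference between arms. In addition, 6.12.6.2 speaks of the rate, not of change from baseline.
3. *One sample per arm against zero.* On the same simulated data this gave p < 10⁻¹² in both arms, which says nothing about the treatment difference.

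None of the three answers objective 16 or 17.

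**Does another SAP section supply a test?** SAP 6.12 has a general line sending continuous safety variables to MMRM or ANCOVA, but the specific sentence in 6.12.6.2 overrides it. No other section names a between-arm test for these rates.

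**Protocol and SAP side by side, objective 16**

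| | Protocol 10.3.4 and synopsis | SAP 6.12.6.2 |
|---|---|---|
| Rate | negative binomial, treatment in model | signed-rank |
| Incidence | logistic, treatment in model | Fisher's exact |
| Reason for change | – | none given |

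**What the regression would give.** For patient *i* with count Yᵢ, exposure Eᵢ days and treatment indicator Zᵢ, log E(Yᵢ) = β₀ + β₁Zᵢ + log(Eᵢ/30). The rate ratio is exp(β₁), with 95% CI exp(β₁ ± 1.96 SE).

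As an illustration, assume 210 per arm, 112 days of follow-up with 12% leaving early, 0.3 events per 30 days, and between-patient variation with mean 1 and variance 1 (gamma). The median simulated SE of the log rate ratio is 0.131. For an estimated ratio of 1.5:

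- 1.96 × 0.131 = 0.257 and exp(0.257) = 1.293
- 95% CI: 1.5/1.293 = 1.16 to 1.5 × 1.293 = 1.94

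A rank test reports neither the 1.5 nor the interval.

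**Why robust standard errors.** Type I error was simulated at nominal 5% over 24 null scenarios with 1,500 runs each. The assumptions were rates of 0.05 to 1.0 per 30 days, between-patient variance 1 or 3, and gamma, log-normal or structural-zero variation.

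| Method | Type I error |
|---|---|
| Rank-sum | 4.0% to 6.2% |
| Negative binomial, robust SE | 4.4% to 6.9% |
| Negative binomial, model-based SE, gamma counts | 4.7% to 6.8% |
| Negative binomial, model-based SE, other counts | 0.0% to 13.9% |

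The model-based version is sound when the counts really are negative binomial and unreliable otherwise. The robust version stays near 5% throughout.

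**The case against.** The best reply is that this is a one-word slip. Reading signed-rank as rank-sum makes the test valid, and a programmer would hit an error with unequal arms. The method change is of a kind the SAP permits, with the reason allowed in the clinical study report, which is not available here. Rank-sum also holds its type I error at least as well as the regression does, so preferring it is not unreasonable.

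Much of that stands. The slip is the likeliest explanation, and rank-sum on exposure-adjusted rates would be a legitimate test. It does not settle the matter: an approved SAP should not need to be guessed at, a rank test gives no rate ratio or interval, and the departure for objective 16 stays unexplained within the SAP.

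A reader might infer more than the documents support:

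- *That the SAP breaks its own rule on justifying changes.* It does not, because SAP 6.1 lets the reason appear in the study report.
- *That the version 2 change list shows the switch was concealed.* That list gives the main changes in SAP Version 2. Its silence says nothing about changes from protocol to SAP.
- *That a rank test would cost power.* The documents give no event rates or dispersion, and the ordering of the methods depends on the count distribution assumed. No power argument is made here.
- *That the incidence analysis is faulty too.* Fisher's exact test is valid, and SAP 6.12 lists it among the defaults for categorical safety variables. Only the reason for replacing logistic regression is missing.

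**Conclusion.** The point holds. As written, SAP 6.12.6.2 has no test that can compare the arms on the rates in objectives 16 and 17, and for objective 16 it departs from the protocol's model without a reason in the SAP. Confidence is high on both, because they rest on the text and on what the signed-rank test is, not on any assumed rate.

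The size is limited. Both are other secondary objectives, and SAP 6.5 makes no multiplicity adjustment for them. Incidence is validly tested, and the primary and multiplicity-adjusted results do not change. What is at stake is a prespecified, interpretable rate comparison for two pump-specific objectives. The interval of 1.16 to 1.94 and the type I error ranges depend on the assumed rates and dispersions and serve only as illustration. The section should be corrected.

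**What to change.** Before unblinding, amend SAP 6.12.6.2 as follows.

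- **Rate, objective 16.** Replace the signed-rank test with negative binomial regression including treatment and a log(exposure days/30) offset. Use robust (sandwich) standard errors for inference and report the rate ratio with its 95% CI. Exposure should cover the same on-treatment days as the events, since Table ITRO 6.2 restricts unplanned changes to the time before IP discontinuation.
- **Rate, objective 17.** Apply the same model. State that the endpoint's >300 mg/dL criterion governs both the rate and incidence analyses; 6.12.6.2 uses it only for a patient-count table. The glossary in Protocol Appendix 1 has ≥300 mg/dL, which differs only at exactly 300 and should be reconciled.
- **Nonparametric support, if kept.** Name it the Wilcoxon rank-sum test on each patient's rate per 30 days.
- **Incidence, objective 16.** Add a clause on why Fisher's exact test replaces the protocol's logistic model.

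The cost is two or three sentences and no new data. The SAP already uses negative binomial regression with an exposure offset for hypoglycemia (6.12.3.1) and CGM episodes (6.13), so the programming largely exists.
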